NIAID	National Institute of Allergy and Infectious Diseases
NIH	National Institutes of Health
PBMC	Peripheral Blood Mononuclear Cells
PD ₂₀	Provocative Dose that causes a 20% fall in FEV ₁
PI	[Site] Principal Investigator
RNA	Ribonucleic Acid
SACCC	Statistical and Clinical Coordinating Center
SAE	Serious Adverse Event/Serious Adverse Experience

Protocol Summary

Full Title:	Urban Environment and Childhood Asthma
Short Title:	URECA
Conducted by:	National Institute of Allergy and Infectious Diseases
Principal Investigator:	[name]
Sample Size:	N=609 originally enrolled
Study Population:	Inner-city children at high risk for development of asthma due to family history, plus a small sample of inner-city children without family history.
Accrual Period:	N/A – Study participants were accrued from 2005-2007
Study Design:	URECA is a longitudinal birth cohort study which is being extended to follow study children to age 17 years.
Study Duration:	Start Date: 1 April 2021 End Date: 31 December 2024
Primary Objective:	To determine the wheezing, asthma and atopy phenotypes in minority children growing up in poor urban neighborhoods as they develop from birth through adolescence.
Secondary Objectives:	
1. To longitudinally analyze the development of lung function and its relationship to asthma.2. To identify which urban exposures (allergens, pollutants, microbes, viral infections, stress) from early life onward affect the development and natural history through adolescence of asthma, allergic rhinitis and allergic sensitization.3. To determine the association of pre-pubertal obesity and the effect of pubertal changes in adiposity and sex hormones on lung growth and asthma onset, prevalence and morbidity.

Exploratory Objectives:

1. To provide samples for analysis and outcomes data for use in mechanistic studies to understand relationships between environmental exposures, changes in immune development, alterations in DNA methylation patterns of airway cells, and the development of allergic sensitization, allergic rhinitis and asthma.
2. To work collaboratively with investigators outside of the NIAID asthma network on mechanistic or clinical studies to test novel hypotheses and to validate, compare and contrast findings from URECA with those in other cohorts or clinical studies.

Endpoints:

Incidence and prevalence of asthma and occurrence of specific phenotypes of asthma

Schematic of Study Design

[figure not shown]

Figure 1. URECA study outcomes. The URECA study began with prenatal assessments of factors that affected early immune development and the development of allergic sensitization and recurrent wheeze during the preschool period. Analysis of data through school age is ongoing, and results to date have related early life environmental exposures to respiratory and asthma phenotypes. Analysis of early life factors that influence allergic rhinitis is in progress. The final stage of the URECA study will extend observations into adolescence, and will focus on factors related to asthma incidence and remission, further definition of allergy and asthma phenotypes, and determine relationships between early life exposures, these outcomes and mechanistic assessments of airway cell gene expression and DNA methylation.

Key Roles

PROTOCOL CHAIR – [name]

[figure not shown]
NIAID MEDICAL MONITOR – [REDACTED]

NIAID PROJECT MANAGER – [REDACTED]

STATISTICIAN – [REDACTED]

1 Background Information and Scientific Rationale

1.1 Background Information

The Urban Environment and Childhood Asthma (URECA) birth cohort study was initiated in 2004 by the Inner City Asthma Consortium (ICAC) to conduct comprehensive studies to define early life exposures that promote the development of disturbances in immune function that will lead to allergic sensitization and asthma.^{1,2} The study recruited a cohort of children from urban areas in economically disadvantaged neighborhoods in New York City, Boston, Baltimore, and St. Louis. The clinical teams collaborated with community leaders and obstetrical groups to recruit a study group representing mothers and children (70% Black, 20% Latino or Hispanic) residing in urban areas of poverty and difficult living circumstances that are reflective of US inner cities.² The overall goal of these studies has been to gain greater insight into the unique effects of the inner-city environment on the development of asthma, and from these findings identify more effective treatments in this high-risk group of children and to begin efforts to prevent the expression of asthma in inner-city youth. The study design focused on collecting data on key environmental exposures (stress, viral infections, allergens, microbes, indoor pollutants), measures of immune development (PBMC cytokine responses, T regulatory cells, allergen-specific IgE and IgG, plasma cytokines), and indicators of clinical outcomes (wheezing episodes, allergic sensitization, medication use, lung function testing). To accomplish these goals, study participants had yearly clinic visits with quarterly phone calls in between.

[figure not shown]
Retention has been highly successful. Despite a historic lack of connection to the medical establishment and atmosphere of distrust of participation in clinical research, the clinical teams used frequent contacts, neighborhood resources, home visits, and an attitude of inclusiveness to maintain retention rates that has far exceeded expectations.³ It is notable that **73% of the children (now ages 13-15 years) remain active participants** (Figure 1, data from November 2020).

The URECA III protocol was completed in March 2017, with the last of the 10-year clinic visits. The follow-on URECA IV protocol ends with the conclusion of ICAC funding on July 31, 2021 when the participants will be between 14 and 16 years old. The current URECA V protocol will be enacted April 1, 2021 and will allow for follow-up of the URECA participants into their 17th year.

1.2 Rationale

Minority children growing up in disadvantaged urban neighborhoods have high prevalence of asthma and burden of disease. Thus, new insights into pathologic mechanisms in early life are needed to improve and direct treatment and to enable prevention. The URECA study has

Figure 1. URECA retention through age 14

collected longitudinal information beginning at birth related to maternal asthma, key environmental exposures (allergens, pollutants, viruses, bacteria, fungi), mechanisms (immune development, airway epithelial cell gene expression, genetics) and outcomes (lung function, allergy, symptoms). Analysis of these data through age 10 years identified clinical presentations (“phenotypes”) of asthma that differ by age of onset, severity, relationship to allergy, lung function and the propensity for exacerbations. For each child, the phenotype reflecting their respiratory health likely results from interactions between heritable factors and environmental exposures. We hypothesize that personal factors (genetics, maternal asthma, hormones) interact with early life environmental exposures at airway mucosal surfaces to modify patterns of DNA methylation (DNAm) and gene expression in airway epithelial cells (AECs), and ultimately AEC function and respiratory health outcomes. Over time, changes in epithelial cell DNAm could lead to modified airway structure and function to influence the risk of developing respiratory allergies and asthma in genetically susceptible children. Because urban minority children have unique environmental exposures and heightened asthma severity and morbidity, it is particularly important to identify specific risk factors and causal mechanisms in these children. To advance beyond recognizing the clinical expression of allergies and asthma (phenotypes) in urban children towards a comprehensive understanding of risk factors and pathologic mechanisms (endotypes), we propose the following **three specific aims** (Figure 2):

Aim 1 will test the hypothesis that genetic and environmental risks for respiratory allergy and asthma phenotypes are mediated through long-lasting epigenetic (DNAm) changes and transcriptional patterns in AECs. We will study genotypes, DNAm, and gene expression in AECs collected from URECA children at ages 11 and 15 years, together with phenotypes and exposures collected longitudinally beginning at birth.

Aim 2 will test the hypothesis that early life exposure to allergens in the home in the absence of a diverse microbiome is associated with sensitization to those allergens and respiratory symptoms (perennial rhinitis and allergic asthma phenotypes). We will identify additional early life exposures that are associated with no sensitization, sensitization without clinical symptoms and sensitization with respiratory symptoms.

Aim 3 will integrate the diverse data available in URECA children to identify asthma endotypes and their predictors by: **a**) using advanced clustering techniques to identify respiratory and asthma phenotypes from longitudinal data, including upper and lower airway symptoms, allergic sensitization, lung function, BMI and psychosocial factors such as depression and risky behaviors; **b**) linking phenotypes to potential causative factors, such as specific environmental exposures (home microbiome and allergen exposure), AEC DNAm and gene expression patterns, upper airway microbial colonization, and serum hormone levels (e.g. insulin, sex hormones, adipokines); and **c**) identifying biomarkers to enable early identification of asthma endotypes.

[figure not shown]

Figure 2. Specific aims (numbered).

The results of these studies will link the pivotal early life exposures to airway epithelial cell DNAm and gene expression patterns, and ultimately to clinical expression of allergic diseases and asthma. These integrated data can be used to detect at-risk children at an early age, and from these pathways, develop and test interventions in early life to prevent allergy and asthma in urban children, and thus relieve a lifetime burden of asthma in this high-risk urban children.

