2.3 Exploratory Objectives

URECA has several exploratory objectives to use data and samples collected from the study participants:

1. To determine the relationships between DNAm and gene expression in AECs collected from URECA children at ages 11 and 15 years, genotypes, and respiratory and allergy phenotypes to age 17 years.
2. To identify which urban exposures (allergens, pollutants, microbes, viral infections, stress) from early life onward are associated with AEC DNAm and gene expression (ages 11 and 15 years) and respiratory and allergy phenotypes to age 17 years.
3. To work collaboratively with investigators in CREW, ECHO and other networks on mechanistic or clinical studies to test novel hypotheses and to validate, compare and contrast findings from URECA with those in other cohorts or clinical studies.

3 Study Design

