10.4.3 Analysis of Exploratory Endpoints

The overall approach to identify phenotypes will be similar to that used with the 7-year and 10-year data sets, using latent class mixed models to identify homogenous subpopulations within sets of longitudinal variable trajectories. Variables characterizing the trajectory clusters (e.g. symptoms, allergic sensitization, lung function and BMI) and other relevant predictors (including demographics) will be used to represent subjects in a Gower distance matrix, which can handle mixed data types. The Akaike information criterion will be used to select the number of clusters (i.e. number of subpopulations) for each variable. These variables will be evaluated for collinearity and variable sets that are highly collinear will be represented by a constituent variable that is most representative of each subset. Children will be clustered to identify distinct phenotypes selected using four criteria: 1) a generalization of the within-clusters sum of squares measure, 2) average silhouette width, 3) Dunn index, and 4) the ratio of average-within versus average-between clusters. In this aim, we will identify asthma endotypes by linking respiratory allergy and asthma phenotypes to mechanistic data, including the patterns of airway epithelial cell DNA methylation and gene expression at 11 and 15 years that will be calculated in Aim 1. Our approach will first assign each subject to one of the phenotypes defined by the approach for Subaim 3.1. We will then conduct an analysis to identify gene expression patterns and

methylation patterns (from ages 11 and 15), and environmental exposures that are characteristic of each phenotype and distinguish among them.

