To identify endotypes, we will use a sparse multinomial logistic regression model. Variables for these models include the DNA methylation and expression modules (Aim 1), and environmental exposures (e.g. viral infections, allergens, microbes, tobacco smoke). Thus, the model will represent endotypes by mapping from biological states and environmental exposures to clinical phenotypes. In a sparse model, the learning algorithm is biased towards selecting a relatively small number of variables. Thus, although we will include a moderately large number of candidate variables in the models, only a sufficient number of variables to distinguish the phenotypes are selected. We will use well established sparse learning methods, such as LASSO and elastic net, which are well suited to high-dimensional data sets that include many potentially irrelevant variables.

We will next identify biomarkers for predicting respiratory allergy and asthma phenotypes that we observe at ages 11 and 15. This analysis will start with subjects clustered according to the phenotypes that we defined in Aim 3.1 and will proceed by inferring functions composed from individual early-life biomarkers that are predictive of the phenotype an individual subject will exhibit. Sparse multinomial logistic regression models will be used to evaluate early life biomarkers. The candidate predictor variables for these models will include (i) demographics, (ii) clinical variables such as wheeze frequency, (iii) gene expression measurements from nasal epithelial cells, and (iv) DNAm measurements from nasal epithelial cells. Aside from demographics, these variables will come from measurements taken during the first three years of life.

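### Section 10.4.3 looks for each phenotype's characteristic exposures in a sparse model that also holds their hypothesised mediators, so an exposure acting through the airway epithelium can be dropped and misread

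*Protocol*

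**What the plan says.** **Hypothesis.** Protocol 1.2 states that personal factors "interact with early life environmental exposures at airway mucosal surfaces to modify patterns of DNA methylation (DNAm) and gene expression in airway epithelial cells". Aim 1 is explicit about the route: "genetic and environmental risks for respiratory allergy and asthma phenotypes are mediated through long-lasting epigenetic (DNAm) changes and transcriptional patterns in AECs". Exposures are upstream, and the airway-cell measurements are the mediators.

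**Question.** Aim 3b in 1.2 is about "linking phenotypes to potential causative factors, such as specific environmental exposures (home microbiome and allergen exposure), AEC DNAm and gene expression patterns". Section 10.4.3 turns this into a search for gene expression patterns, methylation patterns and "environmental exposures that are characteristic of each phenotype and distinguish among them". Exploratory objective 2 (2.3) begins "To identify which urban exposures (allergens, pollutants, microbes, viral infections, stress) from early life onward are associated with AEC DNAm and gene expression" and then asks the same about respiratory and allergy phenotypes to age 17.

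**Model.** Section 10.4.3 says: "To identify endotypes, we will use a sparse multinomial logistic regression model". On its contents: "Variables for these models include the DNA methylation and expression modules (Aim 1), and environmental exposures". On its selection rule: "only a sufficient number of variables to distinguish the phenotypes are selected". LASSO and elastic net are named as possible methods. The section describes a single mapping from biological states and exposures together to the phenotypes. It writes no model with exposures alone.

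**The concern.** If an exposure changes methylation or expression, and that change shapes the phenotype, then the module already carries the exposure's information. A penalised model offered both, and told to keep only what it needs, has reason to keep the module and drop the exposure. The more completely Aim 1 is right, the stronger that pressure.

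The model is sound for telling phenotypes apart. It does not answer which exposures are associated with each phenotype, which is what 10.4.3 and the second half of exploratory objective 2 ask. At stake is a false negative on exposures. Section 1.2 closes by looking to early-life interventions, for which exposures are the natural targets.

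**Working it through.** **1. The plan's own figure.** Section 10.5 gives 442 children at age 14, 73% of 609. Check: 560 + 49 = 609 (section 4.1), and 442/609 = 0.726, which rounds to 73%. The figure reproduces. It is an upper bound for this model, because children with usable nasal cells at both 11 and 15 years may be fewer. The protocol gives no effect size, penalty rule, mediated share or module reliability.

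**2. The structural point.** Let X be an exposure, M its module and Y the phenotype. Under full mediation (X → M → Y), Y is independent of X given M. The population coefficient of X is then zero in a model containing M, while X and Y remain associated marginally. If M is observed with error, X keeps some information. If part of the effect is direct, X keeps that part.

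**3. Simulation inputs.**
- From the protocol: N = 442; six phenotypes (five at age 7 plus one added at age 10, section 3.2.1); LASSO as one named method.
- Assumed: 15 exposures and 25 modules, three of each active; total effect T = 0.6 log-odds per SD of exposure on the linear-predictor scale; exposure–module correlation a = 0.4 or 0.6; mediated share m = 1, 0.5 or 0; module reliability r = 1.0 or 0.6.
- The module's coefficient is mT/a and the direct coefficient is (1 − m)T. For m = 1 the module coefficient is 0.6/0.4 = 1.5 or 0.6/0.6 = 1.0, with direct effect 0. For m = 0.5 it is 0.3/0.4 = 0.75 or 0.3/0.6 = 0.5, with direct effect 0.3.
- The observed module is √r·M + √(1 − r)·noise.
- Fit: L1-penalised multinomial regression, 5-fold cross-validation, 25 replicates per setting. An exposure counts as selected if any of its coefficients is non-zero.

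**4. Share of truly active exposures selected, joint model against exposures alone.**

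| m | r | a | Minimum-CV: joint vs alone | One-SE: joint vs alone |
|---|---|---|---|---|
| 1 | 1.0 | 0.4 | 0.48 vs 0.95 | 0.20 vs 0.61 |
| 1 | 1.0 | 0.6 | 0.49 vs 0.97 | 0.33 vs 0.88 |
| 1 | 0.6 | 0.4 | 0.91 vs 0.97 | 0.63 vs 0.64 |
| 1 | 0.6 | 0.6 | 0.93 vs 1.00 | 0.83 vs 0.93 |
| 0.5 | 1.0 | 0.4 | 0.89 vs 1.00 | 0.72 vs 0.92 |
| 0.5 | 1.0 | 0.6 | 0.88 vs 1.00 | 0.80 vs 0.97 |
| 0.5 | 0.6 | 0.4 | 0.99 vs 1.00 | 0.95 vs 0.96 |
| 0.5 | 0.6 | 0.6 | 1.00 vs 1.00 | 0.93 vs 0.97 |
| 0 | 1.0 or 0.6 | 0.4 or 0.6 | 1.00 vs 1.00 | 0.92–0.97 vs 0.97–1.00 |

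**5. Comparison with noise.** In the two rows with full mediation and error-free modules, pure-noise exposures enter the joint model at rates of 0.44 and 0.39 (minimum-CV) and 0.09 and 0.18 (one-SE). At the minimum-CV penalty, active exposures (0.48, 0.49) are therefore hardly distinguishable from noise. At one-SE they still stand above it (0.20 against 0.09; 0.33 against 0.18).

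**6. Precision.** Each active rate rests on 25 × 3 = 75 selections. Treated as independent, the standard error is at most √(0.5 × 0.5/75) = 0.058. Differences of a few points should not be interpreted; the falls of 40 points or more are well beyond that error. Noise selection was not recorded for the exposure-only fit, so the table compares sensitivity and not overall accuracy.

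**The case against.** **The model's stated purpose is endotypes.** Joint entry is coherent for that goal, and the selection rule is stated openly. This stands, and it is why the joint model should be kept. But the same section also sets out to find the exposures characteristic of each phenotype, and writes no other model for that.

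**Other routes exist.** The first half of exploratory objective 2 relates exposures to methylation and expression, and Aim 1 addresses mediation. Neither step needs to condition on the modules to see an exposure acting on the epithelium. This stands in part: the exposure-to-module link can be recovered there. The exposure-to-phenotype association is not supplied elsewhere. Section 10.4.2.1 models exposures without modules, but for sensitization and rhinitis. Section 10.4.1 promises environmental risk factors for the asthma phenotypes and names no model. The biomarker model later in 10.4.3 does not list exposures. Sections 10.1 and 5.3 defer mechanistic and substudy work to separate plans not shown here. Those plans may fill the gap, but the candidate set criticised here is written in this protocol.

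**The large losses need extreme inputs.** This stands. Nasal-cell modules at 11 and 15 years are unlikely to be complete, error-free carriers of exposures dating from birth. Elastic net tends to keep correlated predictors together and may soften the loss.

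**A stronger reading is not supported.** A reader might infer that exposures acting through the epithelium will be dropped and reported as not characteristic. The protocol does not say how unselected exposures will be reported, and in most simulated settings most active exposures were still selected. Nor is finding exposures the main reason for the extension: its primary objective (2.1) is to determine phenotypes.

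**Conclusion.** The point holds as a mismatch between question and model. Whatever the mediated share, selection in the joint model measures contribution beyond the modules, while the section asks about association with phenotype. An exposure that matters can be dropped and then misread.

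The size is conditional on the assumptions listed. The loss is severe with full mediation and well-measured modules: from 95–97% to 48–49% at the minimum-CV penalty, and from 61–88% to 20–33% at one-SE. With half mediation and no module error it is moderate: from 100% to 88–89%, and from 92–97% to 72–80%. It is mostly small at module reliability 0.6, and little or none without mediation. These figures are for LASSO only.

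The analysis is exploratory and the identification of phenotypes is unaffected. The point is worth correcting because the protocol's own hypothesis is the condition under which the model answers the exposure question worst.

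**What to change.** In 10.4.3, specify the sparse multinomial model in three fits:

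1. Exposures with demographics only, as the analysis that names the exposures associated with each phenotype.
2. Methylation and expression modules only.
3. The joint model, for discrimination and for what exposures add beyond the modules.

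State that non-selection of an exposure in the joint model is not evidence of no association. The first fit needs similar modesty. It estimates association, and as a penalised model it also misses some active exposures (61% selected at one-SE in the weakest setting above).

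The cost is one or two sentences and two extra fits on data already planned. The downside is more exploratory output to report.

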1.3 Potential Risks and Benefits

1.3.1 Risks of Study Procedures

The URECA study has been designated as an observational birth cohort study by the CAUSE consortium and DAIT. As such, this study involves minimal active intervention outside of the normal standard of care for the participant. No study drugs are used in the URECA study. All risks of the URECA study are limited to study procedures, i.e. blood draws, nasal sample collection, allergen skin testing, sputum collection, or pulmonary function tests not included as part of standard of care for this group of patients.

